#### 5.2.3.2 Screening for laboratory evidence of tumour lysis syndrome

Tumor lysis syndrome (TLS) is characterized by a group of metabolic derangements caused by the massive and abrupt release of cellular components into the blood after rapid lysis of malignant cells. The release of intracellular metabolites, including nucleic acids, proteins, phosphorus, and potassium, can overwhelm normal homeostatic mechanisms, potentially leading to hyperuricemia, hyperkalemia, hyperphosphatemia, hypocalcemia, and uremia. This can result in impaired renal function, and in some cases, in acute renal failure and even death (R10-4517). CTCAE classifies TLS in grade 3 (present), grade 4 (life threatening consequences; urgent intervention indicated) and grade 5 (death). Presence of TLS is not clearly defined by CTCAE (R10-4848). For this trial the Cairo-Bishop classification will be used to define presence of TLS, i.e. presence of clinical TLS (R10-4517).

To allow for early treatment in case TLS develops, vigilant monitoring is recommended. Between the first and the second infusion, during the first 48 hours after the start of the second infusion of BI 836826 in course 1 and during the first 24 hours after the start of the infusion(s) in course 2, in between timepoints at which a complete safety laboratory has to be performed, i.e. every 4-8 hours, the following laboratory parameters need to be determined to screen for evidence of a tumour lysis syndrome. In case the schedule as outlined in Section 10.6 is used, monitoring for TLS has to be performed for 24 hours also after the infusion on day 8.

Sampling for TLS in course 3 and subsequent courses should be performed as clinically indicated.

The actual date and time of the blood samples should be recorded in the eCRF.

Haematology	haemoglobin, haematocrit, red blood cell count (RBC), white blood cell count (WBC) with differential, platelets (PLT)
Biochemistry	uric acid, potassium, calcium, inorganic phosphate, lactate dehydrogenase (LDH), creatinine, urea

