The presence of laboratory TLS will be considered according to Cairo-Bishop classification. Under this system, laboratory TLS is investigated based on the serum values of uric acid, potassium, inorganic phosphate, and calcium. TLS is considered to be present if within the time window of 3 days before until 7 days after administration of BI 836826, two or more of these laboratory parameters are abnormal, or change from baseline by ≥25%.

Table 5.4.5.2: 1 Definition of abnormal laboratory values according to Cairo Bishop

Laboratory parameter	abnormal Value	Change from baseline
Uric acid	≥476 µmol/L or 8 mg/dL	≥25% increase
Potassium	\geq 6.0 mmol/L or 6 mg/L	≥25% increase
Inorganic phosphate	≥1.45 mmol/L	≥25% increase
Calcium	≤1.75 mmol/L	≥25% decrease

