6.7 BASELINE, TIME WINDOWS AND CALCULATED VISITS

Study days and visits will be labelled according to the flow chart of the CTP.

Unless otherwise specified, baseline is defined as the time-point closest to but prior to first administration of study medication. If no time is specified and the date is the same as the first administration date, then it will still be considered baseline if not specified otherwise.

Laboratory values: Baseline is defined as the latest time-point before start of the very first administration of study medication. For laboratories where not only the examination date but also time are recorded, examination time has to be taken into account when defining baseline. That is, a laboratory value on the same date as the first study drug administration is considered as baseline value if and only if the time of laboratory value is before or the same as the time of the start of first study drug administration.

If any of these times are missing (either no time of start of first study drug administration or no lab sample stating that it was taken prior to start of first study drug administration) and so it cannot be concluded whether the blood sampling was done before or at the same time of the start of first study drug administration, the last available laboratory assessment before first study drug administration will be taken (Screening laboratory).

For graphical presentations of laboratory data, baseline will be coded as Day = 1.

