7.8.2 Laboratory data

The analyses of laboratory data will be descriptive in nature and will follow the standard procedure laid down in the SOP_"Display and Analysis of Laboratory Data" (5). Patients will be counted under the initial treatment. The analysis of laboratory data will use the same 'analysing treatments' as described for the AEs, except for that the baseline laboratory value (as defined in Section 6.7) will be included in the 'on treatment' period. Patients having at least one post-baseline laboratory value will be displayed in the descriptive analyses. Patients with missing CTCAE grade at baseline or no baseline value but with post-baseline laboratory values will be displayed in the category "Missing CTCAE grade at baseline"

Single time courses by initial treatment will be used to display converted laboratory values over time by dose cohort. The graphs may be truncated if sufficient data is not available. These graphs will be displayed in Chapter 16.1.9.2 for the following parameters.

Haematology: haemoglobin, WBC count and platelets

Differentials: neutrophils (absolute count), absolute lymphocyte count, and natural killer (NK) cells

Enzymes: LDH

Clinically relevant abnormalities (as defined in Section 5.4.5.1) will also be summarised.

Descriptive statistics, including change from baseline, frequency of patients with transitions relative to the references range, will be provided. No post-study laboratory values will be considered. CTCAE grade for applicable laboratory parameters will be calculated according to CTCAE v4.0. The following outputs will be presented:

- Baseline, last value and difference from baseline
- Worst CTCAE grade experienced during the on-treatment period
- Transitions of the CTCAE grade from baseline to the worst lab values, from baseline to the last lab values, and from the worst to last values during the on-treatment period
- Possible clinically significant laboratory values

Note: For calculating the change in CTCAE grade from baseline, patients with a CTCAE grade of -9 (no CTCAE grade defined) will be treated as a CTCAE grade 0 for all analyses. In laboratory listings, the CTCAE grade is displayed as -9.

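### The laboratory TLS rule in SAP 5.4.5.2 accepts pre-infusion, unworsened and non-simultaneous abnormalities, so its frequency can include patients without lysis

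*SAP*

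**What the plan says.** SAP 5.4.5.2 introduces the rule with "The presence of laboratory TLS will be considered according to Cairo-Bishop classification". For uric acid, potassium, inorganic phosphate and calcium, it counts TLS as present if, in a "time window of 3 days before until 7 days after administration of BI 836826, two or more of these laboratory parameters are abnormal" or differ from baseline by at least 25%. The absolute limits, for example "≥476 µmol/L or 8 mg/dL" for uric acid, stand beside the change criterion as an alternative, so meeting one needs no change at all.

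On the reference value, SAP 6.7 states "Baseline is defined as the latest time-point before start of the very first administration of study medication". No per-course baseline is defined, and the TLS rule is not confined to the first administration. On pre-dose data, SAP 7.8.2 uses the on-treatment period for laboratory analyses "except for that the baseline laboratory value (as defined in Section 6.7) will be included in the 'on treatment' period".

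Protocol 5.2.3.2 describes TLS as a "massive and abrupt release of cellular components into the blood after rapid lysis of malignant cells" and equates presence of TLS in this trial with clinical TLS. SAP 7.8.1.3 tabulates clinical TLS from reported adverse events and treats laboratory TLS as an additional analysis.

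**The concern.** The syndrome described in the protocol is abrupt and follows cell lysis, but the flag requires neither onset after the infusion, nor worsening, nor coincidence in time. Comparable rules in the same documents do. Protocol 5.2.2.1 asks for both liver abnormalities in one blood draw. The Hy's law rule in SAP 5.4.5.2 limits the spacing between events. The clinically significant laboratory value rule in that section needs a rise of at least one CTCAE grade from baseline.

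TLS is a protocol-specified significant adverse event, so readers of the report will look at any laboratory TLS count. SAP 7 presents safety data by dose cohort, and the sample size section of the protocol (7.6) assumes cohorts of 1, 3 or 6 patients. In a cohort of six, one false flag is 1/6, or about 17 percentage points. Patients who receive more courses also have more opportunities to be flagged.

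**Working it through.** The plan gives no laboratory TLS rate or analyte variability, so it has no figure to reproduce. The check is a reading of the rule followed by a simulation.

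**Reading the rule**

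1. Window length: 3 + 1 + 7 = 11 calendar days, against a 14-day course (Protocol 4.1).
2. Pre-infusion values: Protocol 6.2.2.1 takes the day 1 safety sample before dosing, so each course's pre-infusion sample falls in its own window. Before the very first dose, SAP 7.8.2 admits the baseline value. That value cannot differ by 25% from itself, but two absolute limits exceeded at baseline are enough.
3. Worsening: none is required for the absolute limits.
4. Simultaneity: no same-sample or spacing condition is stated.

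**Simulation with no drug effect** (40,000 patients per scenario)

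The limits and the 25% rule are from SAP 5.4.5.2, and up to four courses from Protocol 3.1. Everything else is assumed:
- Samples: 6 in course 1, 5 in course 2, 4 in each later course, the first of each being pre-dose.
- Set points: uric acid 330 µmol/L; potassium 4.3, phosphate 1.15 and calcium 2.30 mmol/L.
- Between-patient SDs, same order: 70, 0.3, 0.15, 0.08.
- Within-patient log-SDs, same order: low 6/4/6/2%, mid 10/6/10/3%, high 15/8/15/4%.
- Samples independent within a patient.

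Patients flagged over four courses:

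| Rule | Low | Mid | High |
|---|---|---|---|
| As written | 2.0% | 21.5% | 57.9% |
| Post-infusion samples only | 1.7% | 18.1% | 51.5% |
| Same sample only | 1.1% | 11.4% | 38.4% |
| Course-specific reference only | 2.0% | 24.0% | 67.1% |
| Post-infusion + same sample + worsening, pre-study baseline | 0.5% | 7.3% | 28.7% |
| The same, course-specific reference | 0.5% | 9.0% | 37.7% |

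Repeat runs agree to within a few tenths of a point. In a single course the rule as written flags 0.9%, 10.2% and 33.3%. Pre-infusion samples alone flag 0.4%, 3.0% and 12.6% over four courses.

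**What drives the count**

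- With stationary values, the missing same-sample condition contributes most.
- The worsening condition matters when patients start near a limit. With set points of 420 µmol/L for uric acid and 1.30 mmol/L for phosphate, low variability and one course, 15.6% are flagged as written. Post-infusion, same-sample and course-reference conditions leave 11.4%; adding worsening leaves 1.9%.
- The pre-study baseline inflates the count only if analytes drift. With an assumed +3% per course in uric acid and phosphate (mid variability, four courses), 42.3% are flagged as written and 31.7% with a course-specific reference alone.

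**Sensitivity of the four-course figures**

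- Without between-patient spread, the low case as written falls from 2.0% to 0.1%. With the higher set points, the high case reaches 83.5%.
- Samples taken every 4–8 hours (Protocol 5.2.3.2) are unlikely to be independent. A separate model with no between-patient spread used 12, 6, then 3 samples per course plus one pre-dose each, with somewhat different means and variability. It flagged 0.2/9.4/34.8% with independent samples and 0.1/3.2/16.9% with an assumed within-course correlation of 0.8.

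**Effect in a cohort of six**

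The chance of at least one false flag over four courses is 1 − (1 − p)^6. For p = 0.020 it is 1 − 0.980^6 ≈ 11%; for p = 0.215 it is 1 − 0.785^6 ≈ 77%.

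**The case against.** The strongest defence is that the SAP applies a named published classification, so replacing it would be a matter of preference. Whether the stated window departs from that source cannot be checked from the documents. This stands as a reason to keep the stated count, but does not make that count specific to lysis.

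A second defence is that pre-dose exposure is limited. If only on-treatment laboratory data are used, one baseline sample at most precedes all drug. The flow charts schedule no TLS sampling in the three days before later courses, so 11 of 14 days is calendar coverage rather than sampled coverage. This also stands, and fits the modest contribution of pre-infusion values in the simulation.

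A reader might infer three stronger things that the documents do not support:
- That ordinary variation will be reported as tumour lysis. The output is laboratory TLS, kept apart from clinical TLS.
- That the flag distorts dose decisions. DLT and the MTD do not use it, and dividing the course 1 dose rests on adverse events and DSMB review of safety data (Protocol 4.1). Nor has it been shown that the flag hides a dose relation.
- That comparing every course with the pre-study value is itself a main source of false flags. Under stationary variation, a course-specific reference gives no reduction.

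**Conclusion.** The point holds for the descriptive laboratory TLS frequency. As worded, the rule can flag patients without lysis through pre-infusion values, limits exceeded without worsening, or abnormalities on different days. This is more than missing detail, because the stated rule itself admits these cases.

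The size is uncertain. Roughly 2% to 58% of patients over four courses is the span across the assumed low to high variability, with independent samples and no drug effect. Correlated samples or less spread between patients lower it; set points nearer the limits raise it. These figures show that the count may be hard to interpret; they do not predict this trial's result. SAP 7.8.2 says only that special-interest laboratory values will be analysed, so a breakdown by dose cohort follows from the general rule in SAP 7, not from a specified TLS table.

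**What to change.** In SAP 5.4.5.2, keep the count under the named classification as stated and add a row for treatment-emergent laboratory TLS with three conditions:

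- Only samples after the start of infusion, to day +7, are used.
- At least two of the four parameters meet the criterion in the same sample or within 24 hours.
- A parameter already beyond its limit at the reference value counts only after a further change of at least 25%.

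The SAP 6.7 baseline can remain the reference. A course-specific reference is optional, as a sensitivity analysis if analytes drift over courses.

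The simulation covers the same-sample option; the 24-hour option was not simulated. Even with all three conditions, 7.3% (mid) and 28.7% (high) are still flagged over four courses, so the added row reduces chance flags without removing them.

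The cost is a few sentences and one more derived flag, with no new data collection. The downside is a second, lower count that the report must explain beside the first.

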6. GENERAL ANALYSIS DEFINITIONS

6.1 TREATMENTS

In this Phase I trial, treatments are not randomised (open-label, dose escalation). Different dose levels of BI 836826 are being administered. The data will be presented for all dose cohorts separately and in total over all dose cohorts. To justify the MTD determination, DLTs occurring during the MTD evaluation period (during the first treatment course) will be presented separately from those occurring during the complete on-treatment period.

"Analysing treatment" will be used for reporting of treatment emergent adverse events (AE) and to differentiate between screening, on-treatment, post-treatment and post-study safety data. The inequalities start date \leq onset date of AE < end date will determine whether the AE will be assigned to the "analysing treatment" or not. Table 6.1:1 defines the "analysing treatment period" which will be used for reporting of treatment emergent AEs and safety laboratory parameters. Safety data recorded during the Residual Effect Period (REP) will be considered as on-treatment.

If not specified otherwise, all safety tables will be based on the on-treatment period. AEs that have an onset date during the screening or post-study periods will be displayed in separate listings from those occurred during the on-treatment period.

T 11 (1	1 D C '.'	C 1 .		. 1()
Table 6 1:	I Definition	of analysing	treatment	neriodist
I dolo o.i.	1 Dominion	OI unui yonii 🗲	, u cuuniciit	periodisi

Analysing treatment period	Start date (including)	Stop date (excluding)	
Screening	Date of informed consent	Date of first administration of study medication	
On-treatment	Date of first administration of study medication	Start date of 'Follow-up'	
Follow-up	Date of end of REP +1	Start date of 'Post-study'	
Post-study	Last date patient status obtained / last date patient known to be alive + 1 (if patient is lost to follow-up) / date of refusal + 1 day / the date patient died + 1	During the trial: open / empty; after database lock (DBL): DBL + 1 day	

The initial study medication assigned at the beginning of the first treatment course will be used as the label of the analysing treatment.

The actual dose of study medication administered on the day each AE started will also be derived. This will be presented in patient listings, but will not be used for defining treatments for analysis.

Labels of each analysing treatment period, analysis numbers, the labels used for display in the tables and listings in the CTR, as well as codes, decodes, sort order and labels for each trial medication used in this trial are provided in the TSAP technical document "ADS Plan".

6.2 IMPORTANT PROTOCOL VIOLATIONS

Due to the fact that this is a phase I study, no per protocol population is needed, however important protocol violations (PV) should be identified for patients in the treated set (see Section 6.3). Any PV which may affect safety, efficacy or the patient's rights will be determined.

PVs are summarised into categories and are coded in O*C. The following table defines the different categories of important PVs.

Table 6.2: 1 Important protocol violations

Category /Code		Description	Example/Comment	Exclude d from
A		Entrance criteria not met		
	A1 ¹	Patient has condition that may cause additional risk from study medication	In 5, Ex 3 - 4, 15 - 20	None
	A2 ¹	Patient has laboratory assessments that may cause additional risk.	Ex 8 - 13	None
	A3 ¹	Patient is unable to comply with the protocol	Ex 21, 24	None
	A4 ¹	Patient does not have trial diagnosis or is not part of the target population	In 1 - 4, Ex 1 - 2, 5 - 7	None
	A5 ¹	HIV test not done at screening	See Ex 17	None
В		Informed consent		
	B1 ¹	Informed consent not given or too late	In 7	All
С		Trial medication and randomisation		
	C1 ²	Drug not administered according to the protocol	Administration according to protocol="No" and medical review of associated comments	None
	C2 ²	Drug not administered according to the protocol	Individual pre-medication taken="No" and medical review whether premedication would have been required according to protocol	None

^[1] IPV will be derived automatically

6.3 PATIENT SETS ANALYSED

The Screened Set (SCR) includes all patients who signed the informed consent form and will be used to summarize patient disposition.

^[2] IPV will be identified via individual review at MQRM/BRPM/DBL

The Treated Set (TS): consists of all patients who received at least one application of the BI drug BI 836826. The TS will be used for all planned safety and efficacy analyses.

The MTD evaluation set: This patient set includes all patients who were documented to have received at least one dose of study medication and were not replaced for the MTD evaluation. The MTD evaluation set will be used for the primary analyses of DLTs and MTD determination.

Rules for replacement of patients are defined in Section 3.3.4.1 of the CTP. The list of replaced patients will be provided by the Trial Clinical Monitor no later than the last BRPM and should be attached to the BRPM minutes.

No per protocol population will be used for analyses.

6.5 POOLING OF CENTRES

This section is not applicable because centre/country is not included in the statistical model.

6.6 HANDLING OF MISSING DATA AND OUTLIERS

If not stated otherwise, missing data will not be imputed and remain missing. Potential outliers will be reported and analysed as observed.

Missing or incomplete AE dates are imputed according to BI standards (see "Handling of missing and incomplete AE dates" (2))

If the day of birth date is missing then the imputed day will be the 15th. If start of new CLL therapy date is incomplete (only month given), then the start date will be imputed with the 1st of months unless the first day leads to a date before the stop date of study medication, then the study medication stop date + 1 will be imputed. If more than only the day is missing, dates will not be imputed.

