General safety laboratory parameters 	X	X	X	X	X	Х
Screening for Tumour Lysis Syndrome 	X	X				
Serum pregnancy test 	X				X	
_CMV monitoring 	X			 	x	X
			-			
		1				▏▋
End of active trial treatment					x	┣ ┛ ───
Outcome (remission, progression, death)					X	X
Other therapy for CLL						X

EOT: End of treatment, performed 14 days (± 2 days) after the last administration of BI 836826 FU: Follow-up, starts after EOT, visits at least every 4 weeks until 6 months after EOT, details see Section 6.2.3.2

CMV:

Cytomegalovirus HBV: Hepatitis B Virus

HCV: Hepatitis C Virus

Human Immunodeficiency Virus HIV:

\* the visit number follows the course number, i.e. visit 2 course 1 will read C1 V2 and visit 2 course 2 will read C2 V2 ...

\*\* the planned duration of a treatment course is 14 days

- 1 For AE assessment during FU refer to Sections 5.2.1 and Section 6.2.3.2
- 2 Concomitant therapy during FU only in case indicated for treatment of an AE (Section 4.2.1).
- 3 For details refer to Section 5.2.3.1
- 4 Screening for tumour lysis syndrome in between safety laboratory assessments (Section 5.2.3.2)
- 5 For women of childbearing potential only (please refer to Sections 3.3.3 (exclusion criterion 18) and 5.2.3.1)
- Quantitative CMV DNA PCR or pp65 antigen (Section 5.2.3.3.2) 6

Boehringer Ingelheim BI Trial No.: 1270.1		04 Mar 2015	
	568809-08	Trial Protocol	Page 7 of 111
8	prior to starting treatmen	nent (peripheral blood, clinical) has to be perfo nt, and at day 1 of subsequent courses prior to t ed 1 day earlier to allow for a timely continuation reatment administration.	he next administration of BI
9			

If patients continue beyond cycle 8 in agreement with investigator and BI, the same assessments will be done as applicable for cycle 5-8.

[figure not shown]

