- progressive disease (PD)
- not evaluable (NE)

Best overall response (CR, CRi, PR, SD, PD or NE in this order) is defined as the best overall response obtained since the start of study treatment until PD or start of next CLL therapy. Post-treatment assessments will be considered for the evaluation of best overall response as long as no further CLL therapy has started.

Progression free survival (PFS):

PFS is defined as the time from first treatment with BI 836826 until disease progression or death, whichever occurs first. A patient has an evaluable response assessment if either CR, CRi, PR, SD or PD has been assigned by the investigator.

Derivation of PFS is defined as PFS [days] = date of outcome – date of first administration of BI 836826 + 1.

The censoring rules and the applicable dates of outcome for PFS are given following table.

Table 5.2.2: 1 Derivation rules for progression-free survival

Situation	Outcome (event or censored)	Date of outcome
Disease progression or death	Event	Date of first disease progression or death
No disease progression or death without additional CLL therapy	Censored	Date of last response assessment
No disease progression or death with additional CLL therapy	Censored	Date of last response assessment before start of new CLL therapy
No baseline or post-baseline disease assessment and without death	Censored	Date of first administration of BI 836826
No baseline or post-baseline disease assessment and death on or before second planned disease assessment (i.e. 28 days after first administration of BI 836826)	Event	Date of death
No baseline or post-baseline disease assessment and death after second planned disease assessment (i.e. 28 days after first administration of BI 836826)	Censored	Date of first administration of BI 836826

Failure free survival (FFS):

FFS is defined as the time from first administration of BI 836826 until disease progression or death or start of next CLL therapy.

[figure not shown]
Derivation of FFS is defined as FFS [days] = date of outcome – date of first administration of BI 836826 + 1.

[figure not shown]
The censoring rules and the applicable dates of outcome for FFS are given in following table.

Table 5.2.2: 2 Derivation rules for failure-free survival

Situation	Outcome (event or censored)	Date of outcome
Disease progression or death or start of next CLL therapy	Event	Date of first disease progression or death or start of next CLL therapy

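### A month-only start date of new CLL therapy can be imputed earlier than a visit at which no new therapy had begun, which shortens FFS and excludes that visit from several efficacy endpoints

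*SAP*

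**What the plan says.** SAP 6.6 covers the case in which the month of new CLL therapy is known but the day is not: "the start date will be imputed with the 1st of months unless the first day leads to a date before the stop date" for BI 836826, and "then the study medication stop date + 1 will be imputed" otherwise. It adds: "If more than only the day is missing, dates will not be imputed". The stop date is therefore the only lower bound beyond the month itself.

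Four sets of results in SAP 5.2.2 depend on this start date:

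- **FFS.** The event date is "Date of first disease progression or death or start of next CLL therapy".
- **Best overall response.** This is the "best overall response obtained since the start of study treatment until PD or start of next CLL therapy", and post-treatment assessments count only while no further CLL therapy has begun.
- **PFS censoring.** For a patient without PD or death who received new therapy, the date is "Date of last response assessment before start of new CLL therapy".
- **Lymphocyte and blood-count endpoints.** Values must come at least 8 days after the last infusion, have a reported laboratory response assessment, and precede new CLL therapy.

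The protocol flow chart defines EOT as "End of treatment, performed 14 days (± 2 days) after the last administration of BI 836826". Protocol 6.2.3.2 ends follow-up once the patient receives new anti-neoplastic therapy, and Protocol 4.2.2.1 bars such therapy alongside BI 836826.

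**The concern.** The trial collects dates that can show new therapy had not yet begun: the EOT visit and any follow-up visit attended before the switch. The imputation ignores them. It can place the start of therapy before a visit that the data show to be free of new therapy, and the analysis rules then treat that visit as if it came after the switch.

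If the true start follows the last dose, as the protocol requires, the imputed date is never later than the true one. FFS can only stay the same or shorten, and it can end before a PD that truly came first. Valid assessments can be lost. Efficacy is shown by dose cohort (SAP 7), and Protocol 7.6 assumes escalation cohorts of 1, 3 or 6 patients, so one altered patient can be visible in a cohort's result.

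**Working it through.** The plan states no figure on this point, so there is none to reproduce. The inputs are the SAP 6.6 rule, the EOT window (last dose + 12 to + 16 days) and the SAP 5.2.2 formula, "Derivation of FFS is defined as FFS [days] = date of outcome – date of first administration of BI 836826 + 1". The patients below are illustrative, in a non-leap year.

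**One-course patient.** Doses on 1 and 2 June, EOT with PD on 16 June, new therapy recorded only as June.

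- 1 June precedes the stop date of 2 June, so the imputed start is 3 June, 13 days before EOT.
- FFS = 3 June − 1 June + 1 = 3 days. From the PD date it would be 16 June − 1 June + 1 = 16 days.
- PFS stays an event at 16 days, because the first row of Table 5.2.2: 1 sets no new-therapy condition.
- The only post-baseline assessment now follows the imputed start, so best overall response becomes NE instead of PD.

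**Three-course patients, therapy recorded only as March.** The last column is FFS with the start at the day after EOT, as proposed under the fix.

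| | First dose | Last dose | EOT | True start | Imputed start | FFS, SAP rule | FFS, true start | FFS, EOT + 1 |
|---|---|---|---|---|---|---|---|---|
| A | 3 Feb | 3 Mar | 17 Mar | 30 Mar | 4 Mar | 30 | 56 | 44 |
| B | 26 Jan | 23 Feb | 9 Mar | 25 Mar | 1 Mar | 35 | 59 | 44 |

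These FFS values take new therapy as the first failure event. If EOT showed PD, FFS should be 43 days in both. If there was no PD, PFS censoring should be at EOT (43 days). Under the SAP rule it falls back to the pre-dose assessment of the last course, 28 + 1 = 29 days, which is 14 days earlier.

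**Bounds.**

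- New therapy is the first failure event: a start on the 31st imputed to the 1st loses 30 days (30 × 12 / 365.25 = 0.99 months); a start on the imputed day loses none.
- PD at an on-schedule EOT came first: the stop-date-plus-one branch loses 11 to 15 days (12 − 1 to 16 − 1). If the last dose was on the 1st, the imputed start is that same day and the loss is 12 to 16 days.
- In the stop-date-plus-one branch, every on-schedule EOT falls after the imputed start. In the 1st-of-month branch, EOT is affected only if it lies in the same month as the new therapy.

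**How often an EOT is lost.** The rule was applied to every last-dose date in one year, crossed with true starts 1 to 90 days later, all equally likely. That uniform spread is an assumption. The table gives the share of EOT visits truly before new therapy that the rule excludes, among patients with month-only dates:

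| True start, days after last dose | EOT + 12 | EOT + 14 | EOT + 16 |
|---|---|---|---|
| 17–30 | 62% | 69% | 75% |
| 17–60 | 25% | 29% | 33% |
| 31–90 | 4% | 5% | 7% |

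An EOT on the imputed day itself is counted as excluded. On the same grid the imputed start is on average 13 days early. Where PD was at EOT, FFS is shortened in 18–19% of combinations, by 1.4 to 1.7 days on average over all of them.

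**The case against.** Placing an unknown start at its earliest possible date is a recognised, pre-specified convention. It is cautious for FFS, and in a single-arm trial it is safer to lose an assessment than to credit the drug with a response recorded after other therapy. The analyses are descriptive (Protocol 7.2), and the primary endpoints do not use this date. All of that stands, and it limits the weight of the point. It does not justify overriding a documented visit without new therapy: turning PD into NE, or censoring PFS earlier than the data allow, is not cautious in any useful sense.

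A reader might also infer more than the documents support:

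- **That a PD date proves therapy began later.** Protocol 5.1.2.6 says next therapy may be given without formal PD, so PD alone does not date the switch.
- **That EOT is routinely lost.** It is kept if therapy starts in a later month, and may be kept if EOT data are taken at once when a patient stops mid-cycle (Protocol 6.2.3.1).
- **That the remission rate is generally biased.** Response is assessed after every course and an earlier remission still counts. The rate changes only if the response was first recorded at the excluded visit.
- **That a set number of patients is affected.** The documents give neither the number who switch therapy nor the share with month-only dates.

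**Conclusion.** The point holds in a limited form. SAP 6.6 can assign a start of new CLL therapy that contradicts a visit the trial itself documents. For an affected patient, FFS is shortened by 0 to 30 days where new therapy is the first failure event, and by up to about 12 to 16 days where PD at an on-schedule EOT came first. The visit is also excluded from best overall response, from the PFS censoring date if there was no PD, and from the lymphocyte and blood-count endpoints. FFS is unchanged if PD or death precedes the imputed date. PFS events, MTD and DLT are unaffected.

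This assumes that the true start follows the last dose and that attended visits reliably show whether new therapy had begun. The share of EOT visits lost also rests on the uniform spread of start dates. The overall effect is probably modest and could be nil if few or no dates are month-only.

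**What to change.** In SAP 6.6, impute a month-only start as the latest of:

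- the 1st of the month;
- the study medication stop date + 1;
- the day after the last EOT or follow-up assessment in that month at which no new CLL therapy had been reported.

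Cap the result at the end of the month. Use the same date for FFS, best overall response, PFS censoring and the blood endpoints. Do not use the PD date by itself as a lower bound.

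In patients A and B the imputed start becomes 18 March and 10 March, still 12 and 15 days before the true start, and EOT is kept. If EOT showed PD, FFS returns to 43 days.

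The cost is one SAP sentence and a small programming change using dates already collected. The downside is that the imputed date could be late, and an assessment made after the switch could be counted, if therapy had begun before a visit at which it was not reported. Reporting the number of month-only dates would show whether any of this matters.
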